5.2.3 Conditions for Storage and Use

The Investigator will ensure that both IMPs will be stored in appropriate conditions at room temperature – AMZ001: STORE UPRIGHT 20-25°C (68-77°F) with a permitted excursion of 15-30°C (59°-86°F); Voltaren Arthritis Pain Gel: 20-25°C (68-77°F) with a permitted excursion of 15-30°C (59°-86°F); in a secure location with controlled access. The temperature in the storage area shall be monitored daily on-site when the office is open, and the values shall be documented in a temperature log. Storage and/or transit temperature deviations must be reported to Amzell B.V. without delay. All affected IMP will be quarantined on-site until a determination of acceptability is completed, and approved for use by Amzell B.V.

5.3 Treatment Compliance

5.3.1 Dispensing and Accountability

All handling of medicinal products will be done by trained and authorized personnel at the site. The IMP will only be applied to subjects who meet the eligibility criteria and are allocated as applicable in the study.

The study site will document the dates and quantities (IMPs to be weighed before and after dose application) of IMP applied to each subject and will maintain the batch/lot numbers of the IMP. Subject numbers will be marked on each delivery dispenser (AMZ001) and tube (Arthritis Pain Gel) by the study site and recorded. The monitor will verify the drug accountability during the study and document any discrepancies. Used dispensing packages and tubes will be saved for drug accountability.

5.3.2 Assessment of Compliance

Compliance will be assessed by weighing the dispensing package or tube before and after use daily on-site.

5.4 Prior and Concomitant Therapy

Any prior or concomitant medication will be recorded in the electronic Case Report Form (eCRF) with the main reason for its use.

5.5 Return and Destruction of Medicinal Products

IMP samples assigned as reserve (retention) IMP samples will be maintained at study site until the end of the required retention period, as per US federal regulations 21 CFR § 320.38 and 320.63. Reserve IMP samples will be randomly selected and set aside prior to the beginning of the study enrollment.

When drug accountability has been finalized, verified by the monitor, and signed off by the Investigator, all used and unused IMP (except for the reserve IMP samples retained on site, as per US federal regulations 21 CFR § 320.38 and 320.63) will be sent by study site for destruction in accordance with national requirements.

6. STUDY PROCEDURES

6.1 Study Flow Chart

This same flow chart will be used for all 3 periods; all dosing sequences have the same procedures.

Note: Between Periods 1 and 2 and Periods 2 and 3, there will be a 21-day (+ 7 day) washout

Table 1 - Study Flow Chart for Periods 1, 2 and 3³

| Procedures (Days) | -30 to -2 | Day -1 ² | 1 | 2 | 3 | 4 | 5 | 6 | 7 | 8 ^E |
|--|----------------|---------------------|-----------------|----------------|----------------|----------------|----------------|----------------|-----------------|----------------|
| Screening ¹ | | | | | | | | | | |
| Pre-Treatment Assessments | | | | | | | | | | |
| Informed consent | X ^A | | | | | | | | | |
| Medical history | X | | | | | | | | | |
| Demographics | X | | | | | | | | | |
| Inclusion/Exclusion | X | X | X | | | | | | | |
| Sample Collection | | | | | | | | | | |
| Clinical chemistry, hematology, and urinalysis | X | | | | | | | | | X |
| HIV and HBsAg, Anti-HCV | X | | | | | | | | | |
| Blood samples for PK | | | X ^{BG} | X ^H | X ^F | X ^F | X ^F | X ^F | X ^{BG} | X |
| SPT (FCBP) | X | | | | | | | | | |
| UPT (FCBP) | | X | | | | | | | | X ^I |
| Investigational Medicinal Product (IMP) | | | | | | | | | | |
| Weigh IMP | | | X ^C | X ^C | X ^C | X ^C | X ^C | X ^C | X ^C | |
| IMP application | | | X ^D | X ^D | X ^D | X ^D | X ^D | X ^D | X ^D | |
| Other Assessments/Procedures | | | | | | | | | | |
| Vital signs | X | X | | | | | | | | X |
| Physical examination | X | X | | | | | | | | X |
| ECG | X | | | | | | | | | |
| Baseline Treatment area assessment | X | X | | | | | | | | |
| Assessment of skin reaction | | | X | X | X | X | X | X | X | X |
| Adverse events | | X | X | X | X | X | X | X | X | X |
| Concomitant medication | X | X | X | X | X | X | X | X | X | X |
| Admit / Discharge | | X | | | | | | | | X |

¹Note, only 1 screening will be done before Period 1.

²Day -1 will be repeated after each washout period and before starting Periods 2 and 3 of treatment. ³Use Table 2 at the completion of Period 3.

- A. Subject must sign informed consent prior to any study procedures
- B. On Day 1 and Day 7, Pre-dose (within 1 hour pre-dose) and 2 (± 15 min), 4 (± 15 min), 6 (± 15 min), 8 (± 15 min), 10 (± 15 min), 12 (± 15 min), 14 (± 15 min), 16 (± 15 min), 18 (± 15 min), 20 (± 15 min), and 24 (± 30 min) hours (on Days 2 and 8) post initial application
- C. Before and after dosing
- D. As specified for the assigned treatment regimen
- E. If a subject prematurely withdraws from the study at any time, all attempts should be made to complete the following: reason for withdrawal; assessment of skin reaction; weigh IMP container; physical examination; vital signs; clinical laboratory safety tests; AEs and concomitant medication.
- F. Collect PK blood sample prior to morning dosing (within 1 hour pre-dose).
- G. On Day 1 and 7, if Voltaren Arthritis Pain Gel applications overlap with PK collections, blood samples will be obtained prior to each Gel application.
- H. Day 2 pre-dose will be the same collection as 24 hours post application on Day 1.
- I. Only conducted on Day 8 of Period 3 (EOT visit) or Early Termination (ET) visit.

At the end of Period 3, there will be three additional PK blood samples taken respectively at 3 weeks (21 days), 4 weeks (28 days), and 5 weeks (35 days) after the last application to compare elimination phase of AMZ001 vs. Voltaren Arthritis Pain Gel and to further describe the elimination phase of the AMZ001 product. During this follow-up period, subjects will not be confined to the study site. Subjects will be reminded on the restrictions to be followed as part of concomitant medications prior to being discharged on Day 8 of this 3rd period.

Table 2 - PK Outpatient Visits

| PK Outpatient Visits (Post Period 3) | 3 Weeks (21 days) ±2 days | | 4 Weeks (28 days) ±2 days | | 5 Weeks (35 days) ±2 days |
|--------------------------------------|------------------------------|--|------------------------------|--|------------------------------|
| Sample Collection | | | | | |
| Blood samples for PK | X | | X | | X |
| Other Assessments/Procedures | | | | | |
| Adverse events | X | | X | | X |
| Concomitant medication | X | | X | | X |

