4.4 Withdrawal Criteria

The following medical and other reasons justify a premature termination (by subject or Investigator) of any of the IMPs:

- Withdrawal of informed consent,

- Serious adverse event (SAE)/AE,
- Allergic reaction to the study materials,
- Subject's request,
- Occurrence of one of the safety criteria for exclusion after treatment has been instituted,
- Subject is lost to follow-up, and/or
- Investigator's judgment.

The subjects have the right to withdraw from the study at any time for any reason, without the need to justify their decision. However, the Investigator should record the reason for the subject's withdrawal, if possible. The Investigator also has the right to withdraw subjects if the Investigator considers that the study treatment may compromise the safety of the subject or the subjects' non-compliance may impact the interpretation of the study results.

For any discontinuation, the Investigator will perform the follow-up examinations, obtain all the required details, and document the date of the premature termination and the main reason in the electronic Case Report Form (eCRF).

Data obtained after the subject has withdrawn his/her consent cannot be entered into the database. This also applies to biological samples drawn prior to the withdrawal of the consent but not analyzed at the time of the withdrawal, unless the subject consents to the use of these data.

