8. ADVERSE EVENTS

8.1 Adverse Event (AE) Definition

An AE is any untoward medical occurrence in a subject participating in a clinical study. It includes:

- Any unfavorable and unintended sign, symptom or disease temporally associated with the use of the IMP, whether or not considered to be caused by the IMP.
- AEs commonly observed, and AEs anticipated based on the pharmacological effect of the IMP.
- Any laboratory abnormality, vital sign or finding from physical or other examinations assessed as clinically significant by the Investigator [Note: findings from assessments and examinations done during screening are not AEs but are recorded as medical history.]
- Accidental injuries, reasons for any change in medication (drug and/or dose), reasons for any medical, nursing or pharmacy consultation, or reasons for admission to hospital or surgical procedures.

- Overdoses and medication errors with and without clinical consequences.

All pre-treatment events will be captured as medical history.

A treatment emergent AE (TEAE) is defined as any AE occurring after start of IMP administration and within the time of residual drug effect (5 days), or a pre-treatment AE or pre-existing medical condition that worsens in intensity after treatment with the IMP and within the time of residual drug effect.

A post-treatment AE is defined as any AE occurring after the first dose of study drug and until the last study visit (end-of-study visit) or until 3 weeks post dose (whichever is longer).

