8.2 Collection and Recording of Adverse Events

8.2.1 Collection of Adverse Events

The Investigator must monitor the health of the subject throughout the study from the time of enrolment until the last study visit.

The sources of AEs cover:

- The subject's response to questions about his or her health (a standard non-leading question such as "How have you been feeling since your last visit?" is asked at each visit).
- Symptoms spontaneously reported by the subject.
- Investigations and examinations where the findings are assessed by the Investigator to be clinically significant changes or abnormalities.
- Other information relating to the subject's health becoming known to the Investigator (e.g., hospitalization).

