8.5 Follow-up of Adverse Events and Serious Adverse Events

8.5.1 Follow-up of Adverse Events with Onset during the Study

During the study, the Investigator must follow-up on each AE until it is resolved or until the medical condition of the subject is stable.

After the subject's last visit, the Investigator must follow-up on any AEs that occurred during the study classified as serious or considered to have a reasonable possible causality to the IMP with the outcome "Not recovered" until resolved or until the medical condition of the subject is stable. All such relevant follow-up information must be reported to Amzell B.V. If the event is a chronic condition, the Investigator and Amzell B.V. may agree that further follow-up is not required.

Collection of SAEs with Onset after Last Visit

If an Investigator becomes aware of a SAE after the subject's last visit and assesses the SAE to have a reasonable possible causality to the IMP, the case will have to be reported to Amzell B.V., regardless how long after the end of the study this takes place. Such reports will be considered for expedited reporting and managed as such.

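### No adverse event contact is scheduled after early termination, so the protocol's own 5-day and 3-week AE windows are not actively covered for subjects who stop during or soon after a dosing week

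*Protocol*

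**What the plan says.** **Early leavers.** Protocol section 6.1, footnote E: "If a subject prematurely withdraws from the study at any time, all attempts should be made to complete the following". The list that follows includes AEs and concomitant medication, but no day relative to the last application and no further visit or call. Footnote I mentions a termination visit only when placing the urine pregnancy test: "Only conducted on Day 8 of Period 3 (EOT visit) or Early Termination (ET) visit". Section 4.4 adds: "For any discontinuation, the Investigator will perform the follow-up examinations, obtain all the required details". It gives neither content nor timing for those examinations.

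**Completers.** Table 2 schedules AE and concomitant-medication contacts at 21, 28 and 35 days (±2) after the last application. It is headed as post Period 3, and footnote 3 of Table 1 brings it in once Period 3 is complete. After Periods 1 and 2, a continuing subject is asked about AEs at the next Day -1, which follows a washout of 21 days (+7).

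**AE windows.** Section 8.1 defines a TEAE as "any AE occurring after start of IMP administration and within the time of residual drug effect (5 days"), with a further limb for pre-existing conditions that worsen. It runs post-treatment AEs "until the last study visit (end-of-study visit) or until 3 weeks post dose (whichever is longer").

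**Duty to collect.** Section 8.2.1: "The Investigator must monitor the health of the subject throughout the study from the time of enrolment until the last study visit".

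**AEs already found.** Section 8.5.1: "During the study, the Investigator must follow-up on each AE until it is resolved or until the medical condition of the subject is stable". Beyond the last visit, this duty continues for unrecovered AEs that are serious or possibly related.

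The SAP (section 10.6) tabulates TEAEs by the most recently applied treatment. It adds no AE follow-up for subjects who withdraw.

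**The concern.** Section 8.1 sets AE windows that run past the last dose, and section 8.2.1 stops looking for AEs at the last visit. For a completer this does no harm, because the last visit comes well after both windows have closed. For a subject who stops mid-week and is assessed then, the last visit may be the termination visit. Collection then ends before the windows that the protocol itself defines.

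Safety and tolerability is a secondary objective. Section 4.4 lists AEs and allergic reactions among the reasons for withdrawal, and section 1.2 names application-site reactions as a risk. Subjects who stop for such reasons are of particular safety interest, and they would have the shortest scheduled AE ascertainment. If withdrawals differed by product, new TEAEs would be missed more often on the product with more withdrawals.

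**Working it through.** **1. How many subjects the plan allows for.** Sections 3.2 and 9.1 give 60 evaluable subjects and a 20% dropout and non-evaluable rate. 60 / (1 − 0.20) = 75, which reproduces the planned number randomized. The allowance is 75 − 60 = 15 subjects.

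**2. Where the 3-week limb applies.** A completer's last visit is at day 35 (33 to 37) after the last application, already beyond day 21. The 3-week alternative in section 8.1 therefore matters only for a subject whose last visit comes earlier. Among dosed subjects, that means those who leave early. Sections 8.1 and 8.2.1 give the same answer for completers and different answers for this group.

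**3. Days without a scheduled AE contact.** Let d be the day of the termination assessment, counted from the last application. The protocol does not fix d, so each value below is an assumption.

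- TEAE days not covered = max(0, 5 − d)
- Post-treatment days not covered, taken to day 21 = max(0, 21 − d)
- Shortfall against a Period 3 completer = 35 − d

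| d | TEAE days not covered | Post-treatment days not covered | Shortfall against 35 days |
|---|---|---|---|
| 0 | 5 of 5 | 21 of 21 | 35 |
| 1 | 4 of 5 | 20 of 21 | 34 |
| 3 | 2 of 5 | 18 of 21 | 32 |
| 5 | 0 of 5 | 16 of 21 | 30 |
| 7 | 0 of 5 | 14 of 21 | 28 |
| 21 | 0 of 5 | 0 of 21 | 14 |

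A contact at day 21 or later brings both window columns to zero whatever d is, because section 8.2.1 has subjects asked how they have been since their last visit.

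**4. Ceiling on person-time.** Suppose all 15 stop during dosing and are assessed on the day of their last dose. Then 15 × 5 = 75 TEAE person-days and 15 × 21 = 315 post-treatment person-days have no scheduled contact. For scale, 60 completers with three periods of 7 dosing days plus 5 days contribute 60 × 3 × 12 = 2,160 TEAE person-days, and 75 / 2,160 = 3.5%. This is a ceiling before replacements.

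**5. Which output each window feeds.** Protocol section 9.7.6 puts only TEAEs in the summary tables and lists post-treatment AEs separately. The 5-day shortfall can change per-treatment counts. The 3-week shortfall can change listings only.

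**The case against.** A reader might infer that early leavers have no contact at all after termination. The documents do not support that:

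- Section 4.4 requires follow-up examinations after any discontinuation.
- Section 8.5.1 follows recorded AEs to resolution or stability and, after the last visit, those that are unrecovered and serious or possibly related. A subject who stops because of an AE has a recorded AE, so follow-up continues while it qualifies.
- Under section 8.5.1, related SAEs that the investigator learns of are reportable at any time. Section 8.4.1 covers deaths within four weeks of treatment ending.
- Section 9.2 says that enrolled subjects are followed to completion.

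All of this stands. None of it schedules a contact at which a new, non-serious AE would be sought. Section 4.4 gives no timing, section 8.5.1 concerns events already recorded or SAEs that happen to become known, and section 9.2 gives no mechanism.

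A second objection is that full loss of both windows is itself an assumption. That is right. Footnote E states neither the number nor the timing of assessments, and a subject who leaves late in washout may be assessed after one or both windows have closed.

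A third concerns size. The 20% includes non-evaluable subjects, so 15 does not count withdrawals during dosing. Subjects who withdraw consent to contact cannot be followed under any wording. This also stands.

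Finally, section 9.7.6 refers to a Safety Management Plan, which is not among the documents reviewed, for how follow-up will be done. The summary given there covers coding and tabulation. The plan may contain a later contact, but the protocol text does not.

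**Conclusion.** The point holds for dosed subjects who withdraw during or shortly after a dosing week. The gap is in the active search for new non-serious AEs after termination. It arises because the timing of the termination assessment is undefined, nothing is scheduled after it, and section 8.2.1 closes collection before section 8.1's windows end.

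The size depends on an unstated day. With termination 0 to 1 day after the last dose, 4 to 5 of 5 TEAE days and 20 to 21 of 21 post-treatment days have no scheduled contact. At day 7 it is 0 of 5 and 14 of 21, and from day 21 none. Fewer than 15 of the planned 75 are likely to be affected, although replacements under section 4.5 could add some.

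It would be tempting to conclude that TEAE rates will be biased between products. The documents give no withdrawal rates by product, so a differential effect is possible but not shown. Only the 5-day shortfall could produce one. The point has no bearing on the primary pharmacokinetic comparison. It merits correction because two sections disagree for an identifiable group and the remedy is cheap.

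**What to change.** - **Footnote E and section 4.4:** add one AE and concomitant-medication contact, by telephone if convenient, no earlier than 21 days after the last application, for every dosed subject who leaves early. Exempt subjects who withdraw consent to contact and those whose termination visit is already that late.
- **Section 8.2.1:** end AE collection at the later of the last study visit and 3 weeks post dose, to match section 8.1.

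With this contact in place, coverage no longer depends on when the termination visit falls. If the Safety Management Plan already schedules such a contact, the protocol should state it.

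The cost is a short amendment and at most about 15 calls before replacements, with no added samples or clinic visits.

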6.2 Study Procedures

All subjects **must** provide written informed consent prior to any study procedures.

6.2.1 Screening (Days -30 to -2)

The following procedures will be performed or reviewed at this visit:

- Informed consent
- Medical history
- Demographics
- Inclusion/Exclusion criteria
- Treatment area assessment
- Physical examination
- Vital signs
- Clinical laboratory safety tests (clinical chemistry, hematology, and urinalysis)
- HIV, HBsAg and Anti-HCV
- SPT (for FCBP)
- 12-lead ECG
- Concomitant medication

6.2.2 Day -1

Day -1 will be repeated after each washout period and before starting Periods 2 and 3 of treatment.

The following procedures will be performed or reviewed:

- Inclusion/Exclusion criteria
- Vital signs
- Physical exam
- UPT (for FCBP)
- Baseline treatment area assessment
- AEs
- Concomitant medication
- Subjects will then be admitted into the study site

6.2.3 Days 1, 7, and 8

Subjects in each dosing sequence (1-6) will begin treatment at this visit and 24-hour PK samples will be collected.

The following procedures will be performed or reviewed:

- Assessment of treatment area prior to Randomization (Period 1, Day 1 only)
- Inclusion/Exclusion criteria
- Randomization (Period 1, Day 1 only)
- Weigh Voltaren Arthritis Pain Gel container or AMZ001 dispenser – before and after dosing (Day 1 and Day 7)
- IMP application according to respective treatment period and dosing sequence (Day 1 and Day 7)
- Vital signs (Day 8)
- AEs
- Concomitant medication

- Assessment of skin reaction prior to the first application on Day 7 and on Day 8 (approximately 24 hours after the first application on Day 7)
- Physical examination (Day 8)
- Blood samples for PK on Day 1 and Day 7: Pre-dose (within 1 hour pre-dose) and at 2 (± 15 min), 4 (± 15 min), 6 (± 15 min), 8 (± 15 min), 10 (± 15 min), 12 (± 15 min), 14 (± 15 min), 16 (± 15 min), 18 (± 15 min), 20 (± 15 min), and on Day 8 approximately 24 (± 30 min) post initial application on Day 7. Day 2 pre-dose will be the same collection as 24 hours post application on Day 1.
- UPT (for FCBP) (Day 8)
- Clinical chemistry, hematology, and urinalysis (Day 8)
- Then discharged from the study site (Day 8)

6.2.3.1 Day 2, 3, 4, 5, and 6

Subjects in each dosing sequence (1-6) will continue treatment and one PK sample will be collected prior to dosing.

The following procedures will be performed:

- Weigh Voltaren Arthritis Pain Gel container or AMZ001 dispenser – before and after dosing
- Assessment of skin reaction prior to the first application of the day
- IMP application according to respective treatment period and dosing sequence (Day 2, 3, 4, 5 and 6)
- AEs
- PK blood sample – within 1 hour pre-dose in the morning. The Day 2 pre-dose will be the same collection as 24 hours post application on Day 1.
- Concomitant medication

Note: Between Periods 1 and 2 and Periods 2 and 3, there will be a 21-day (+ 7-day) washout, and the subjects will not be confined to the study site.

At the end of Period 3, there will be three additional PK blood samples taken respectively at 3 weeks (21 days), 4 weeks (28 days), and 5 weeks (35 days) (see [Table 2](#)) after the last application to compare elimination phase of AMZ001 vs. Voltaren Arthritis Pain Gel and to further describe the elimination phase of the AMZ001 product.

7. STUDY ASSESSMENTS

Laboratories will provide Laboratory Manuals that will cover all blood and urine tests and describe sampling and shipment procedures including contact details, storage conditions, equipment, volume, analytical method, reference ranges, etc. The laboratory manuals will be provided to the clinical investigational unit before the start of the study.

